6.1.5 Suspected unexpected serious adverse reactions

A suspected unexpected serious adverse reaction (SUSAR) is an unexpected adverse drug reaction which also meets the definition of serious adverse events.

6.2 Methods of recording and assessing adverse events

Few adverse events have been reported following albendazole, ivermectin or moxidectin administration in STH-infected individuals. The most common adverse events were abdominal cramps, headache, fatigue, nausea, diarrhea, fever and vertigo [7, 8, 17, 36-38].

The observation time for AE starts when the treatment is initiated. Subjects will be kept for observation for at least 3 hours following treatment for any acute AE and. If there is any abnormal finding, the local study physician will perform a full clinical examination and findings will be recorded. An emergency kit will be available on site to treat any medical conditions that warrant urgent medical intervention. Participants will also be interviewed at 3h and 24h as well as retrospectively 14 -21 days, 5-6 weeks and 3 months after treatment about the occurrence of AEs.

Information on all AE (incidence, intensity, seriousness and causality) will be entered immediately in the source document, and also in the appropriate AE module of the case report form. For all AEs, sufficient information will be pursued and/or obtained so as to permit i) an adequate determination of the outcome of the event (i.e. whether the event should be classified as a SAE); and; ii) an assessment of the causal relationship between the AE and the study treatments. Intensity of AE will be judged by the study physician, following guidelines by the European Medicine Agency (Note for Guidance on Clinical Safety Data Management).

All SAE, unexpected adverse drug reactions or SUSARs must be reported as described in Section 6.3.

6.3 Reporting of serious adverse events

Any study-related unanticipated problem posing risk of harm to subjects or others (including all unexpected adverse drug reactions), and any type of serious adverse event (SAE) will be immediately (within a maximum of 24 hours after becoming aware of the event) notified to the study sponsor-investigator and co-PIs:

[name]. [name] (Sponsor-investigator)

Swiss Tropical and Public Health Institute

[name]

[contact]

[contact]

E-mail: [contact]

[name] (Co-PI)
Public Health Laboratory Ivo de Carneri
[name]
[contact]
[contact]
[contact]
Email: [contact]

Within the following 48 hours, the local co-investigator must provide to study sponsor-investigator further information on the serious adverse event or the unanticipated problem in the form of a written narrative. This should include a copy of a completed SAE form, and any other diagnostic information that will assist the understanding of the event. In exceptional circumstances, a serious adverse event may be reported by telephone. In these cases, a written report must be sent immediately thereafter by fax or e-mail. Names, addresses and telephone for serious adverse event reporting will be included in the trial-specific SAE form. Relevant pages from the CRF may be provided in parallel (e.g., medical history, concomitant medications).

All pregnancies must be reported to the Sponsor-Investigator promptly after becoming aware of the pregnancy. Treatment will not be administered at follow-up time points in the event of pregnancy. A study physician recruited from a local health facility/ hospital will serve as medical contact. The treating physician will follow up on the study participant until the pregnancy is resolved. The outcome of the pregnancy must be reported to the Sponsor-Investigator.

6.4 Safety reporting to Health Authorities and Ethics Committees

The sponsor-investigator will send appropriate safety notifications to Health Authorities in accordance with applicable laws and regulations. Additionally, this information will be provided to 'Ethikkomission Nordwest- und Zentralschweiz' (EKNZ, Switzerland), and the 'Zanzibar Health Research Ethics Review Committee' (ZAHREC, Tanzania) in Zanzibar according to national rules. Fatal or life-threatening serious adverse events or SUSARs will be reported within 24 hours followed by a complete report within 7 additional calendar days. Other SAEs and SUSARs that are not fatal or life-threatening will be filed as soon as possible but no later than 14 days after first knowledge by the sponsor.

7. Data management and data quality control

The investigators are responsible for an adequate data quality. Prior to the initiation of the study, a short investigator's meeting will be held between investigators of Swiss TPH and PHL-IdC. This meeting will include a detailed discussion of the protocol, performance of study procedures (SOPs from previous studies available on site), CRF completion, specimen collection and diagnostic methods.

Information about study subjects will be kept confidential and managed accordingly. Screened participants will be listed in a confidential "subject screening log" and attributed a unique study number. Enrolled participants will be listed in a confidential "subject enrolment log"; this document will constitute the only source to decode the pseudonymized data and will only be accessible to the investigators. CRF data will be double-entered and compared using Beyond Compare 4 (Scooter Software Inc., Madison, Wisconsin). Any discrepancies will be reviewed against the hard copies of the CRF and corrected accordingly. Electronic data files will be stored on secured network drives with restricted access for study personnel only. Data analysis will be conducted with pseudonymized data and reporting of findings will be fully anonymized.

Essential infrastructure such as a locked room for safe storage of hardcopy data will be made available.

7.1 Source data

Source data are comprised of clinical findings and observations as well as laboratory data maintained and compiled at the study site. Source data are contained in source documents and are allowed to be accessed by local authorities. Source data will be directly entered in the following documents:

1. CRF: Primary data collection instrument for the study. It holds records of all clinical and physical examination data, treatment information, AEs, and infection status at the follow-up time points. For every subject enrolled in the clinical trial, a corresponding CRF exists. All data requested on the CRF must be recorded, and investigators will review and approve each CRF for completion.
2. Laboratory parasitology sheets: Record of the STH egg counts at all sample collection time points
3. PK: Time records of PK samplings for 60 willing participants

7.2 Data collection and documentation

Data collected and produced within this trial will fall into one of the following categories:

- a) Egg counts of *T. trichiura*, Hookworm (*Necator americanus* and *Ancylostoma duodenale*, no differentiation between the two species will be made) and *A. lumbricoides* derived from standard Kato-Katz microscopy performed at baseline as well as at 14-21 day, 5-6 weeks and 3 months post-treatment.
- b) Egg counts of *T. trichiura*, Hookworm and *A. lumbricoides* derived from FECPAK-G2 platform analysis at baseline and 14-21 days post-treatment.
- c) Anthropometric and clinical characteristics of the trial participants collected using the study's CRF such as weight, height, blood pressure, temperature, pregnancy status (for female subjects), overall health status and any abnormal medical condition or chronic disease.
- d) PK time recording of each sample per person
- e) Measured concentrations analyzed from micro blood samples and subsequently derived PK/PD parameters
- f) Infection status of *T. trichiura*, Hookworm and *A. lumbricoides* derived by PCR assessment of ethanol-fixated stool sample aliquots

Data of categories c) and d) will be recorded both paper-based and directly into tablets using CommCare (Dimagi, Inc., Cambridge, MA) or a comparable data-entry software, whereas data in categories a), b) and e) will be captured by software only. Data compiled using the software will be directly saved on the personal, password-protected laptop of one of the Co-PIs and uploaded to a server hosted at Swiss TPH, Basel. In paper-based data collection, all missing data must be explained. If an item on the CRF is left blank because the procedure was not done or the question was not asked "N/D" will be entered. If the item is not applicable to the individual case "N/A" will be written. All entries will be printed in black ink. All corrections must be noted with the initials of the respective team member and dated. Data in categories a) and c) will be merged into a masterfile and saved in .xlsx, .mdb and/or .csv. Data in categories b) and d) - f) will be saved as .mdb, .csv, .xlsx, .txt and/or .pdf files. For categories a) – d), paper-based data will serve as physical backup. Hard copies of the data such as parasitological sheets and CRFs will remain at PHL-IdC. Digital copies along with single databases and compiled masterfiles will be transferred to the Swiss TPH, Basel. Data will then be analyzed as described in section 8.

7.3 Ethical, legal and security issues

Screened participants will be listed in a confidential “subject screening log” and attributed a unique study ID. In case of enrolment, participants will be listed in a confidential “subject enrolment log” utilizing the same study IDs. The codes will be linked with the participant’s identity on a separate file (subject identification list), filed in a secured place at PHL-IdC and will only be accessible to investigators. Personal data will be coded for data analysis. No names will be published at any time, and published reports will not allow for identification of single subjects. Confidentiality will be ensured throughout the entire research project. All databases will be password secured. None of the investigators declare to have any conflicts of interest.

7.4 Data storage and preservation

All samples will be destroyed after completion of the study. Paper-based and electronic source data and related material will be preserved for a minimum of 15 years to enable understanding of the study procedures, which allows the work to be assessed retrospectively and repeated if necessary. The study site will retain a copy of the documents to ensure that local collaborators can provide access to the source documents to a monitor, auditor, or regulatory agency. Electronic source documents will be stored on a flash drive and kept at the study site (IdC PHL, Pemba, Tanzania). The primary data storage and backup will be in the Swiss TPH shared server and secondary data storage will be on personal, password-protected laptops of [name], [name] and [name], and on SWICTHdrive (a cloud storage supported by University of Basel). Electronic data files and archiving conditions will be made strictly confidential by password protection.

7.5 Study documents: translations – reference language

- The protocol master document will be in English, all further language versions are translated thereof
- The ICF master document will be in English, all language versions are translated thereof.

8. Statistics

8.1 Definition of primary endpoint

Egg reduction rate calculated from the geometric means of co-administered moxidectin/ albendazole and ivermectin/ albendazole against *T. trichiura* assessed at 14-21 days post-treatment is the primary endpoint in our study.

8.2 Justification of number of trial subjects

For the primary analysis the trial is designed as 2 arm parallel group randomized-controlled trial. We test the primary hypothesis that the treatment combination moxidectin and albendazole is not inferior compared to ivermectin and albendazole. To determine the required sample size, we run a series of simulation using artificial data which behaved roughly in the same way as found by [7]. Assuming true ERR of 98% in both arms and 98.5% in both arms, we estimate that 160 participants are required in each group to be at least 90% sure that the limits of a two-sided 95% confidence interval will exclude a difference in favor of the standard group of more than 2 percentage points. To account for a potential loss to follow-up of 10% and including a safety margin of 20% to account for uncertainty in our assumptions underlying the simulations, we anticipate enrolling 210 participants in each combination treatment arm (arm A and B). Secondary hypothesis will compare monotherapies against the combinations. Assuming cure rates below 25% for albendazole and ivermectin and 40% for moxidectin monotherapy respectively, we need to enroll 20, 20 and 80 children, respectively, to identify a statistical significant difference with 85 to 90% power (arm C, D, E) [1, 5, 8, 39]. We thus aim to recruit 210 + 210 + 20 + 20 + 80 = 540 participants in total.

The suggested sample size of a maximum of 4 PK samples from 60 willing participants (10-15 per study arm) is sufficiently high to determine the population PK parameters and investigate drug-drug interactions with a sparse sampling scheme, considering that PK variability is moderate. A moderate PK variability is a reasonable assumption when dealing with adolescents.

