Storage of data and samples for future research aims	After the study has been completed, all samples will be destroyed. Case report forms and electronic source data will be kept for a minimum of 15 years.
Conflict of interest in relation to the investigated drugs	We declare no conflict of interest in relation to the investigated drugs.

2. Background information

Albendazole and mebendazole are the most widely used drugs for preventive chemotherapy campaigns against soil-transmitted helminth (STH) infections. Albendazole is characterized by high cure rates (CRs) against infections with *Ascaris lumbricoides* (96%) and hookworm infections (80%). Mass drug administration (MDA) with single dose albendazole has already been considered insufficient to achieve World Health Organization (WHO) goals of morbidity reduction, in the case of *Trichuris trichiura* infections due to the low efficacy of this drug (CR 31%) [1, 2].

Therapies combining two or more drugs are widely advocated in different therapeutic areas such as tuberculosis, malaria, HIV/AIDS or cancer. The underlying rationale for multifactorial pharmacological treatment varies with the disease and includes the protection against the selection of drug-resistance, and hence, a prolongation of the life-span of effective and available drugs, and to increase and broaden the efficacy over drugs being administered in monotherapy [3].

To help prioritize candidate STH combinations, the Bill & Melinda Gates Foundation (BMGF) defined different levels of investment risk. In more detail, the prioritization includes four tiers and takes into account (i) the current efficacy and safety data of existing anthelmintic drugs; (ii) the financial and time investment required to generate the necessary evidence to change WHO treatment guidelines; and (iii) the potential for transformational change. The ivermectin/ albendazole combination was identified as a first-tier priority. Moxidectin/ albendazole was classified as second tier priority (since at this stage the drug was not yet approved).

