5.1 Recruitment

The study will be carried out in adolescents aged 12-19 years attending secondary schools on Pemba Island, Tanzania. Schools in areas with moderate to high *T. trichiura* infection intensities will be selected and identified based on experience from earlier studies and/or knowledge of the local collaborating teams. The trial will be implemented as a school-based study in order to simplify recruitment of adolescents. Caregivers of potential participants and adolescents aged ≥ 18 years will be invited to participate in an information session. The research team will explain the purpose and procedures of the study, as well as potential benefits and risks of participation. Attendees will be encouraged to ask questions which will be discussed in an open setting.

Caregivers interested in having their child/children of 12-17 years of age participate in the study or adolescents aged 18-19 years willing to participate will be invited to complete the process of informed consent by signing the informed consent form (ICF). In addition, written assent will be obtained from underage participants. Participants having a signed ICF will be assessed for eligibility during screening procedures.

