5.2 Inclusion criteria

1. Aged between 12 and 19 years.
2. Written informed consent signed by either parents/caregivers for underage adolescents (aged 12-17 years) or by the participant him/herself (18-19 years of age); and written assent by underage participant.
3. Agree to comply with study procedures, including provision of two stool samples at the beginning (baseline) and on three follow-up assessments (14-21 days, 5-6 weeks and 3 months after treatment).
4. Willing to be examined by a study physician prior to treatment.
5. At least two slides of the quadruple Kato-Katz thick smears positive for *T. trichiura* and infection intensities of at least 48 EPG.

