8.3 Description of statistical methods

In non-inferiority trials, non-inferiority has to be demonstrated in the intention-to-treat and in the per protocol population. The primary analysis will be performed according to the intention-to-treat principles using the available case population which includes all participants with any primary end point data. Subsequently, a per-protocol analysis will be performed. EPG will be assessed by calculating the mean egg count from the quadruplicate Kato-Katz thick smears and multiplying this number by a factor of 24. The ERR will be calculated as:

$$ERR = 1 - \frac{\frac{1}{n} e^{\sum \log(EPG_{follow-up} + 1)} - 1}{\frac{1}{n} e^{\sum \log(EPG_{baseline} + 1)} - 1}$$

Geometric mean egg counts will be calculated for the different treatment arms before and at 14-21 days after treatment to assess the corresponding ERRs. Bootstrap resampling method with 5,000 replicates will be used to calculate 95% confidence intervals (CIs) for ERRs and the difference between the ERRs. CRs will be calculated as the percentage of egg-positive children at baseline who become egg-negative after treatment. Differences among CRs will be assessed by using unadjusted logistic regressions. In a subsequent analysis an adjusted logistic regression (adjustment for baseline infection intensity, age, sex, weight) will be performed.

Questionnaires on physical functioning and treatment satisfaction will be evaluated by creating summary scores by summing up and transforming the single question scores according to the following formula: [(actual raw score-lowest possible raw score)/(possible raw score range)]*100 [40].

Adverse events will be summarized in frequency tables and compared between treatment groups using descriptive statistics.

To assess differences in diagnostic performance of the different tools used as compared to the standard Kato-Katz microscopy (FECPAK-G2 and/or PCR) a readily available hierarchical Bayesian egg-count model will be applied to the individual level data.

A nonlinear mixed-effects (NLME) modelling will be used to determine pharmacokinetic parameters. Concentrations are measured with a validated LC-MS/MS method [20, 31]. Using NLME, the key population PK parameters will be calculated based on which an effect on the drug-drug interaction will be determined:

- C_{\max} maximal plasma concentration
- t_{\max} time to reach C_{\max}
- AUC area under the curve, from 0 to 24h and 0 to inf.
- $t_{1/2}$ elimination half-life

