11.2 Data and safety monitoring board (WHO) / data monitoring committee (EU/FDA)

In our study, no data and safety monitoring board will be established, since we work with well-known drugs in a small sample size and using a single dose treatment. However, advisors will be informed regularly and the findings discussed.

12. Dissemination of results and publication

The final results of this study will be published in a scientific journal and presented at scientific conferences. BMGF will be acknowledged as study funder. All results from this investigation are considered confidential and shall not be made available to any third party by any member of the investigating team before publication. A summary of study conclusions will be shared with ZAHREC. After publication, study results will be made available to study participants.

13. References

1. Moser, W., C. Schindler, and J. Keiser, *Efficacy of recommended drugs against soil transmitted helminths: systematic review and network meta-analysis*. BMJ, 2017. **358**: p. j4307.
2. Farrell, S.H., et al., *Investigating the Effectiveness of Current and Modified World Health Organization Guidelines for the Control of Soil-Transmitted Helminth Infections*. Clin Infect Dis, 2018. **66**(suppl_4): p. S253-S259.
3. Hughes, D. and D.I. Andersson, *Evolutionary consequences of drug resistance: shared principles across diverse targets and organisms*. Nat Rev Genet, 2015. **16**(8): p. 459-71.
4. WHO, *The selection and use of essential medicines: report of the 21st WHO Expert Committee*, in *WHO Technical Report Series*. 2017, World Health Organization: Geneva.
5. Palmeirim, M.S., et al., *Efficacy and safety of co-administered ivermectin plus albendazole for treating soil-transmitted helminths: A systematic review, meta-analysis and individual patient data analysis*. PLoS Negl Trop Dis, 2018. **12**(4): p. e0006458.
6. Patel, C., et al., *Efficacy and safety of ivermectin and albendazole co-administration in school-aged children and adults infected with *Trichuris trichiura*: study protocol for a multi-country randomized controlled double-blind trial*. BMC Infect Dis, 2019. **19**(1): p. 262.
7. Barda, B., et al., *Efficacy and tolerability of moxidectin alone and in co-administration with albendazole and tribendimidine versus albendazole plus oxantel pamoate against *Trichuris trichiura* infections: a randomised, non-inferiority, single-blind trial*. Lancet Infect Dis, 2018. **18**(8): p. 864-873.

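### Does the 31% albendazole cure rate in section 2 undermine the power stated for arm C in section 8.2?

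*Combined protocol and SAP*

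**What the plan says.** Section 8.2 sets the sizes of arms C (albendazole), D (ivermectin) and E (moxidectin) from assumed cure rates: "Assuming cure rates below 25% for albendazole and ivermectin and 40% for moxidectin monotherapy respectively, we need to enroll 20, 20 and 80". The purpose is "to identify a statistical significant difference with 85 to 90% power (arm C, D, E) [1, 5, 8, 39". Each combination arm has 210 participants. The allowance that begins "To account for a potential loss to follow-up of 10" percent is described for the two combination arms only. The section gives no combination CR, significance level or sidedness for these comparisons.

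Section 2, explaining why mass treatment with single-dose albendazole falls short against *T. trichiura*, says this is "due to the low efficacy of this drug (CR 31%) [1, 2". Reference 1, cited in both sections, is listed in section 13 as a "systematic review and network meta-analysis".

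Section 5.1 describes the trial population as "adolescents aged 12-19 years attending secondary schools on Pemba Island, Tanzania", and section 5.2 requires "infection intensities of at least 48 EPG" together with at least two positive slides out of four. For the analysis, section 8.3 says: "Differences among CRs will be assessed by using unadjusted logistic regressions".

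**The concern.** A rate of 31% is not below 25%. The protocol quotes two albendazole cure rates against the same parasite, cites reference 1 in both places, and does not say why the planning value is the lower one. The lower value flatters the power calculation, because a weaker monotherapy leaves a larger difference to detect.

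Albendazole is a component of both combinations, so arm C is a comparator for both in secondary objective a. With 20 participants it is small, and its power is sensitive to the assumed CR. If the background rate held in this trial, the stated 85 to 90% would be too high. A non-significant comparison with albendazole would then be read against a power figure that the design did not have.

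**Working it through.** **Inputs from the documents.** Arm C 20, arm E 80, each combination arm 210. Albendazole CR 25% (the upper bound in section 8.2) or 31% (section 2). Moxidectin CR 40%. Stated power 85-90%.

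**Assumptions, because section 8.2 is silent.** Two-sided 5% (z = 1.96), and one combination CR, *c*, for all comparisons.

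**Formula.** Two-proportion power with pooled variance under the null:

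power = Φ[(d − 1.96·s0)/s1]

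Here d = c − p; s0 = √[p̄(1−p̄)(1/n1 + 1/n2)] with p̄ the pooled rate; s1 = √[p(1−p)/n1 + c(1−c)/n2].

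**Step 1: infer the combination CR from arm E.** Solve for *c* with p = 40%, 80 v 210.
- 85% power: c = 59.5% (d = 0.195, s0 = 0.0655, s1 = 0.0644, argument 1.036).
- 90% power: c = 61.0%.

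**Step 2: reproduce the plan's figure for arm C at 25%** (20 v 210).
- c = 59.5%: d = 0.345, s0 = 0.116, s1 = 0.103, argument 1.147, power 87.4%.
- c = 61.0%: d = 0.360, argument 1.307, power 90.4%.

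Solving from arm C instead gives c = 58.4-60.8%. One combination CR near 60% therefore accounts for both arms, and the stated 85-90% is internally coherent.

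**Step 3: replace 25% by 31%.**
- c = 59.5%: d = 0.285, s0 = 0.116, s1 = 0.109, argument 0.533, power 70.3%.
- c = 61.0%: d = 0.300, argument 0.684, power 75.3%.

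**Step 4: 10% loss in every arm** (18, 72 and 189; *c* re-solved as 60.5-62.1%). Arm C has 85.9-89.2% at 25% and 69.0-74.1% at 31%.

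**Step 5: sensitivity to the albendazole CR** (no loss; with loss).

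| Albendazole CR | 20 v 210 | 18 v 189 |
|---|---|---|
| 20% | 96-97% | 95-97% |
| 25% | 87-90% | 86-89% |
| 31% | 70-75% | 69-74% |

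Arm C keeps 85% power up to a CR of 26.0-27.5% without loss, or 25.4-26.9% with it.

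**Step 6: sensitivity to what section 8.2 leaves out, at 31%.**
- Without the arm E link: 50-54% at a combination CR of 55%, and 82-86% at 65%.
- One-sided 5%, *c* re-solved: 75-80% without loss, 74-78% with it.
- Exact enumeration of the unadjusted logistic regression, *c* re-solved for each test: Wald 69-74% (68-73% with loss), likelihood ratio 71-75% (69-74%). The same tests give 84-90% at 25%.
- Other approximations at 20 v 210, with *c* kept from step 1: unpooled 74.5-78.9%, log-odds Wald 65.3-69.8%, continuity-corrected 61.1-66.7%, Fisher about 64-69%.

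**Step 7: could 31% and 85% both hold?** That needs c = 64.6%. Arm E would then have about 97% power with 80 participants, outside its stated 85-90%.

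**The case for a change.** The strongest case for a change is that the mismatch is in the current text and affects a stated figure. The inference of a combination CR near 60% is not arbitrary, since one value fits arms C and E together. Every variant that uses it stays below 85% at 31%. There is almost no slack above the planning bound, and the only other albendazole rate in the protocol lies 6 points above it (31 − 25). A sentence in section 8.2 would cost little.

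The arithmetic stands, and so does the missing explanation. The step from there to an overstated power does not. It needs 31% to be the expected rate in this trial, and section 2 does not offer it as that. The figure explains why albendazole alone is inadequate in mass treatment, and by its title reference 1 is a pooled analysis. The trial enrols infected Pemba adolescents above an intensity threshold, and a planning value for that group may fairly differ from a general one. The shared citation proves little: in section 8.2 four references close a sentence that covers three monotherapy rates, and any of them could be the source of the albendazole value. The documents do not allow that to be checked in either direction.

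The transfer from arm E is also less secure for one of the two comparisons. Arm E corresponds to moxidectin/albendazole, whereas arm C is compared with ivermectin/albendazole as well, and arm E says nothing about the CR of that combination.

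**Conclusion.** The concern does not call for a change. Section 8.2 delivers its 85-90% on its own inputs: 87-90% for arm C at 25%, or 86-89% with 10% loss. The 31% in section 2 is a general rate that can stand beside a lower planning value for this population. What is missing is a sentence of justification and the unstated combination CR and significance level.

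As a sensitivity scenario only: if 31% applied, a single combination CR of about 60% held for both combinations, and the test were two-sided at 5%, arm C power would be roughly 69-75%, or about 61-80% across the test methods and sidedness tried. Without the arm E link the spread is about 50-86% for combination CRs of 55-65%.

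The planning rate enters only the sizing of arm C. The analysis in section 8.3 does not use it, and the observed rates with their confidence intervals will show how informative the comparison was. Arms D and E, the primary non-inferiority sizing and total enrolment of 540 are unaffected. A fuller account in section 8.2 would help a reader, but it would alter nothing that is done or concluded.
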